**Please save frequently**

- c) Describe the study design (e.g., single/double blind, parallel, crossover, control, experimental, observational, etc.). If the study is investigator-initiated, a timeline for individual subject recruitment, follow-up, and analysis for the study is required. Also, indicate if the subjects will be randomized.

Our study is a prospective comparison between absorbable hemostatic agents as a group and the body's natural hemostatic ability without aid of therapy in patients undergoing bilateral sinus surgery with or without septoplasty.

We calculated the sample size and power analysis in the following way:

Given the number of statistical tests, we calculated a Bonferonni correction to set the alpha for the analysis at 0.017 (alpha originally at .05 divided by the number of tests = .05/30 = 0.017). Using G-Power statistical software, power analyses were completed using the Means: Wilcoxon-Mann-Whitney test (two groups). Given alpha at 0.017 and Power at 0.80, we determined that a total of 244 participants (122 in the control group, 122 in the hemostatics group) would be needed to detect a medium effect size (d=0.5). Since one nostril will be used as the control and the therapy applied to the other side, the number of participants needed drops to 122.

Based on previous studies, we conservatively expect a dropout rate of 15%. In order to maintain the same number of participants, we would need to enroll a total of 144 participants

Postoperatively, patients will rate subjective symptoms such as nasal obstruction, bleeding,

**Protocol Title:** Analysis of hemostatic agents compared to physiologic hemostasis

---

pain, and nasal discharge on a scale ranging from 1-10, of which 10 is the most severe. Similarly, the treating physicians on endoscopic examinations will rate objective measures such as mucosal edema, infection, time spent debriding, and synechiae formation. (Please see the attached patient and physician questionnaires) Patient questionnaires will be completed on postoperative days #1, 2, 7, and 14. Surgical healing outcomes will be noted during routine postoperative visits 1 and 2 weeks after surgery. Expected total duration of each subjects' participation is 6 weeks. Total subject accrual should take no longer than one year. Data analysis will take up to three months. Estimated time of completion is 03/2018.

d) **If subjects will be given placebo, please justify placebo use. \*?HELP?\***

N/A

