**If No, explain what SLU will NOT participate in:**

**Please save frequently**

Page numbers from a sponsor's protocol/grant may be referenced in 3b, 3c, and 3d.

- b) **Describe all the procedures, from screening through end-of-study, that the human subject must undergo in the research project, including study visits, drug treatments, randomization and the procedures that are part of standard of care. Specify which procedures are for research and which are standard of care. Please note: The box below is for text only. If you would like to add tables, charts, etc., attach those files in the Attachment section (#16).**

a.) Patients will have (standard of care) Endoscopic Sinus Surgery.  
 b.) Each patient will receive a hemostatic agent in one nostril and nothing in the other nostril.  
 c.) Products will be placed in patients' post-operative sinus cavities at the end of the procedure according to company recommended instructions. Essentially all products placed in the middle meatus are allowed to remain there until absorbed or removed at a post operative visit on weeks 1, 2, and 6. Post-operative irrigations (Standard of Care) will remove much of the material. Any residual material is removed in the office on normal, (Standard of Care) post-operative debridement on weeks 1, 2, and/or 6.  
 d.) Subjects will provide subjective pre- and post-operative data, such as rating their pain, bleeding, obstruction, and discharge on days 0, 1, 2, 7, and 14 (Standard of Care).  
 e.) Patients will be given a questionnaire packet pre-operatively (Research Related). Questionnaires will include post-operative data on days 0, 1, 2, 7, and 14. They are asked to bring completed questionnaires on standard post-operative visits.  
 f.) The physician will record objective and subjective data (synechiae, edema, infection, granulations, and time spent debriding) upon regular reexamination of the sinuses after surgery, at post-operative visits on weeks 1, 3, and 6. All procedures are standard clinical care.  
 g.) Follow up visits will conform to standard clinical care; patients will be seen in the physician's clinic.

**Protocol Title:** Analysis of hemostatic agents compared to physiologic hemostasis

---

clinic.

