- c) If the proposed study is a clinical trial where a drug, vaccine, device or other treatment is compared to a placebo group or comparison treatment group, what are the guidelines or endpoints by which early decisions regarding efficacy or lack of efficacy can be made? For example, it may be reasonable to stop enrollment on a study when efficacy has already been clearly demonstrated, to avoid unnecessary enrollments of additional subjects. Alternatively, it may be reasonable to stop enrollment when it is clear that efficacy will never be demonstrated, given the statistical power of the study as designed. Describe the guidelines that are in place to assist in making these determinations, if relevant to the proposed study.

If side effects or discomforts do occur, [name] and/or [name] will try to minimize and treat these by irrigating the treated sinus with saline to remove the Arista, Nexfoam, Sinufoam, Nasopore, Posiseq, or Posiseq X.

- d) Describe how data analysis will be performed (statistical tests, methods of evaluating data) and indicate the smallest group/unit for which separate reporting will occur. For studies involving a questionnaire, if data and reliability information are available, please describe or provide references. For full board, unfunded studies describe sample size determination and power analysis. If none, please justify.

Means and standard deviations will be obtained for data collected from patients and the physician. These outcomes will be used for comparative evaluation of hemostatic agents (n=144) against no therapy. Statistics will include descriptive statistics and a non-parametric ANOVA comparing the questionnaire patient data and the physician data followed by Post-hoc multiple comparisons.

Please save frequently

- e) State if deception (including incomplete disclosure of study purpose/procedures) will be used. If so, describe the nature of the deception and provide a rationale for its use. Also, describe debriefing procedures or justify a waiver of the requirement to debrief. NOTE: for studies using deception, an alteration of consent must be justified in the Informed Consent section of the protocol (#13) and the debriefing script/statement must be uploaded in the Attachments section (#16). See IRB Deception Guidelines.

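### The treated and untreated nostrils belong to the same patient, but section 3d names no paired test for that contrast, only a non-parametric ANOVA of unstated type

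*Combined protocol and SAP*

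**What the plan says.** Section 3b(b) of the protocol fixes a split-nose design: "Each patient will receive a hemostatic agent in one nostril and nothing in the other nostril". Sections 2a and 2c describe the study as a comparison of absorbable agents, taken as a group, with untreated healing. Section 3d repeats that aim, a "comparative evaluation of hemostatic agents (n=144) against no therapy", but names no test in that sentence. The next sentence gives descriptive statistics and "a non-parametric ANOVA comparing the questionnaire patient data and the physician data followed by Post-hoc multiple comparisons".

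The only specific test is in the sample-size text of 2c: "power analyses were completed using the Means: Wilcoxon-Mann-Whitney test (two groups". There the split-nose design is used to halve 244 to 122 patients, and nothing is said about how the two sides will be compared. No section names a signed-rank, sign, McNemar, Friedman or mixed-model analysis.

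**The concern.** Two nostrils of one patient are not independent observations. Section 8h requires comparable disease on both sides, so positive correlation between a patient's two scores is plausible. The wording of 3d allows at least two kinds of test:

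- **Independent-groups ANOVA (Kruskal-Wallis).** With two groups this is the Mann-Whitney test. It ignores the pairing. Under positive correlation its standard error is too large, so real differences are more easily reported as no difference.
- **Related-samples ANOVA (Friedman).** This respects the pairing. With two conditions it reduces to a sign test, which uses the direction of each patient's difference and discards its size.

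Post-hoc comparisons normally follow a factor with three or more levels, perhaps agents or days, but 3d does not say which. The test of the main contrast is thus left to be chosen at analysis.

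**Working it through.** **Inputs.** From 2c: d = 0.5, power 0.80, 122 per group, 15% dropout, and the alpha line "alpha originally at .05 divided by the number of tests = .05/30 = 0.017". The quotient is 0.05/30 = 0.00167, so both 0.00167 and the printed 0.017 are carried below. Assumed, because the protocol does not give them: the within-patient correlation ρ (0, 0.3, 0.5), sidedness, and normal data.

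**Step 1. Reproduce the plan's size.** Noncentral-t power for the Wilcoxon-Mann-Whitney test, with n scaled by 3/π:

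- α = 0.00167, one-sided: 122 per group (power 0.801). This matches 2c.
- α = 0.00167, two-sided: 136 per group.
- α = 0.017: 75 (one-sided) or 89 (two-sided) per group.
- Dropout: 122/0.85 = 143.5, so 144. This matches.

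**Step 2. Is the halving to 122 sound?** For paired data d_z = d/√(2(1−ρ)), which is 0.354, 0.423 and 0.500 at ρ = 0, 0.3 and 0.5. A signed-rank test, one-sided at 0.00167 with 80% power, needs 125, 89 and 65 pairs. The 122 is close to the ρ = 0 figure.

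**Step 3. Unpaired test on paired data.** The variance it assumes is too large by a factor of about 1/(1−ρ). Its actual false-positive rate at nominal 0.05 is therefore about 2{1 − Φ(1.96/√(1−ρ))}:

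- ρ = 0.3: 1.96/0.837 = 2.34, giving 1.9% (simulated: about 2%).
- ρ = 0.5: 1.96/0.707 = 2.77, giving 0.6% (simulated: about 0.6%).

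**Step 4. Two-condition Friedman as a sign test.** The chance that a patient's difference favours the better side is p = Φ(d_z) = 0.638, 0.664 and 0.691. At two-sided 0.00167 (critical z 3.14) the observed fraction must exceed 0.5 + 3.14 × 0.5/√122 = 0.642. Power is Φ((p − 0.642)/√(p(1−p)/122)):

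- ρ = 0: (0.638 − 0.642)/0.0435 = −0.09, power 0.46.
- ρ = 0.3: (0.664 − 0.642)/0.0428 = 0.51, power 0.69.
- ρ = 0.5: (0.691 − 0.642)/0.0418 = 1.17, power 0.88.

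**Step 5. The three tests side by side.** Simulated power, 122 pairs, two-sided; d = 0.3 is illustrative and is not a target in 2c.

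| α | d | ρ | Unpaired | Signed-rank | Friedman (2 conditions) |
|---|---|---|---|---|---|
| 0.00167 | 0.5 | 0 | 0.74 | 0.72 | 0.46 |
| 0.00167 | 0.5 | 0.3 | 0.77 | 0.91 | 0.69 |
| 0.00167 | 0.5 | 0.5 | 0.80–0.81 | 0.98 | 0.88 |
| 0.00167 | 0.3 | 0.5 | 0.11 | 0.50 | 0.28 |
| 0.017 | 0.5 | 0.5 | 0.97 | 1.00 | 0.97 |
| 0.017 | 0.3 | 0.5 | 0.44 | 0.79 | 0.57 |

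**The case against.** The case for the plan has four parts.

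1. *A non-parametric ANOVA may be a related-samples one.* True. A reader might infer that the plan specifies an unpaired analysis. The text does not show that, and the Mann-Whitney test appears only in the sizing. The concession does not settle the matter, because the two-condition Friedman reading has less power than the signed-rank test throughout the table, and less than the unpaired test at ρ = 0 and 0.3 with α = 0.00167 and d = 0.5.
2. *The ANOVA clause should not be taken to contrast patients' ratings with physicians' ratings.* This stands. The preceding sentence of 3d sets agents against no therapy, so the natural meaning is that the ANOVA is applied to both data sets.
3. *The harm at the design effect is limited.* Partly right. At 0.017 and ρ = 0.5 the unpaired test still has 0.97 power at d = 0.5. Under positive correlation it is conservative, so the documents do not support a charge of inflated false positives. That would need negative correlation, and 8h points the other way.
4. *The patient scores may not be side-specific.* This cannot be checked: the protocol says "Please see the attached patient and physician questionnaires", and those attachments are not in the public document. If a symptom has one overall score per patient, no test can compare the sides on it.

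A reader might also infer that halving 244 to 122 was an error. Step 2 shows it is close to a paired calculation at zero correlation.

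**Conclusion.** The point holds as a fault of specification with a measurable consequence. The design is paired, the contrast is stated, and no paired test is attached to it. At two-sided 0.00167 and d = 0.5, the tests that 3d allows range in power from 0.46 to 0.74 when the sides are uncorrelated, and from 0.69 to 0.91 at ρ = 0.3. For any positive correlation examined, the signed-rank test is the most powerful of the three. At ρ = 0 it is about 1 to 2 points below the unpaired test. The size rests on assumed values of ρ, normal data and two-sided testing. It shrinks to little at the printed 0.017 with d = 0.5 and ρ = 0.5. It should be fixed before analysis, but it does not undermine the enrolment figure.

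**What to change.** In 3d, keep the descriptive statistics and replace the ANOVA clause with:

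> For each post-operative outcome and time recorded separately for each nostril, the within-patient difference (agent side minus untreated side, all agents pooled) will be tested with the Wilcoxon signed-rank test (zero differences by Pratt's method) and reported with the mean or median paired difference and its confidence interval; yes/no outcomes will be tested with the exact McNemar test. Comparisons between agents are exploratory and use the within-patient differences (Kruskal-Wallis across agents).

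State which questionnaire items are scored per nostril. Outcomes with one overall score per patient are descriptive only. Where many differences are zero the median can be zero despite a real shift, so the mean is the safer summary there.

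**Separate points.** These are not settled by this wording:

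- the alpha arithmetic (0.05/30 is 0.00167, not 0.017);
- one- or two-sided testing;
- the status of day 0, where 3b(d) has "Subjects will provide subjective pre- and post-operative data" and 3b(e) has "Questionnaires will include post-operative data on days 0, 1, 2, 7, and 14";
- the physician assessments, at weeks 1 and 2 in 2c but weeks 1, 3 and 6 in 3b(f). These times must be reconciled before the tests can be counted.

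**Cost.** Wording only, for outcomes already recorded per nostril. At ρ = 0 the signed-rank test gives up about 1 to 2 points of power at the same alpha. With heavily tied scores it gives up a few more: about 4 with Pratt's method if 60% of untreated sides are assumed to be at the lowest score (0.476 to 0.440, or 0.616 to 0.576, depending on the direction of effect). If two-sided testing at 0.00167 is also adopted, power at ρ = 0 and d = 0.5 is about 0.72, against the 0.80 that 122 gives one-sided, and should be restated.

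Item 8(c) of the expedited-review section marks remaining work as data analysis only. The change should therefore be dated before the two sides are compared, or reported as made after data collection.

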**\*\*\* Radioisotopes or Radiation Machines \*\*\***

You have not selected the Radioisotopes option in the General Checklist. If you would like to add Radioisotopes information, please select the option to enable this section.

**4. Radioisotopes or Radiation Machines**

In this section, investigators must enter all radiation usage associated with the protocol.

Important: Protocols that involve non-standard of care radioactive materials (which includes the terms "radioisotopes", "radionuclides", "radiopharmaceuticals", and "nuclear medicine studies", e.g., "PET", "MUGA", "Zevalin", and/or specific radionuclides such as "F-18", "Tc-99m", "Th-201", "I-131", "Ra-223", "Y-90", etc.) will receive review by the Radiation Safety Officer (RSO) and/or Radiation Safety Committee (RSC). In these cases, submission to the RSO/RSC should occur first, even before submission to IRB. For more information on how to submit for radiation safety review, see RSC instructions or contact the Radiation Safety Officer at [name].

(1) It is the responsibility of the PI to assure the accuracy and completeness of the data submitted in this section, consistent with guidelines provided below. (2) For projects requiring radiation procedures, please refer to this guidance.

a) If applicable, list and quantify the radiographic diagnostic and therapeutic procedures associated with this protocol by clicking "Add" and adding to Table 1 below. (Includes X-ray, fluoroscopy, CT, radioactive materials, nuclear medicine, PET-CT, radiation oncology, accelerator, Cyber Knife procedures, etc.)

b) Total estimated research radiation dose \* :

\* Calculate from the table above by adding the Effective Dose Subtotals for all procedures.

**Protocol Title:** Analysis of hemostatic agents compared to physiologic hemostasis

---

NOTE: Informed Consent Radiation Exposure Risk Statement- The applicant must insert the appropriate Informed Consent Radiation Exposure Risk Statement template language into the SLU IRB Informed Consent, inclusive of applying the total estimated research radiation dose specified in item b) from the table above, as instructed in the SLU IRB Informed Consent Template. Contact the IRB Office at [name] or [contact] with any questions.

---

**\*\*\* Devices \*\*\***

**5. Devices**

a) Please list in the space below all investigational devices to be used on subjects during this study.

b) Please list in the space below all FDA approved devices to be used on subjects during this study.

**FDA Approved Devices**

Device Name	Manufacturer	Provide IDE #. Documentation of IDE # required unless imprinted on sponsor protocol (attach in section #16).
Arista	Medafor	exempt
Nexafoam	Hemostasis	exempt
Sinufoam	Arthrocore	exempt
Nasopore	Polyganics	exempt
Posisep Hemostat Dressing	Hemostasis	exempt
Posisep X Hemostat Dressing	Hemostasis	exempt

- Device Name** Arista
- Manufacturer** Medafor
- Describe the device to be used and attach the device manual in section #16.**  
hemostatic agent
- Provide the PMA approval or 510(k) clearance number or attach letters in section #16.**
- Does the research involve use of a commercially available device for an unapproved purpose?**
- This device research is:**Note: Attach documentation/justification in section #16. Exempt from IDE regulations, (submit required attachments)

**Protocol Title:** Analysis of hemostatic agents compared to physiologic hemostasis

---

Non-Significant risk, (submit required attachments)

Significant risk, (submit required attachments)

The risk determination should be based on the proposed use of a device in an investigation and not on the device alone.

- 7. Provide IDE #. Documentation of IDE # required unless imprinted on sponsor protocol (attach in section #16). See Guidance. exempt
- 8. Who holds the IDE? (Could be manufacturer, study sponsor, or an individual investigator acting as the 'sponsor'). Medafor
- 9. If a SLU Investigator is serving as sponsor-investigator of the IDE, click Yes to assure that the additional FDA requirements will be followed. Yes, the additional FDA requirements will be followed.

- 1. Device Name Nexafoam
- 2. Manufacturer Hemostasis
- 3. Describe the device to be used and attach the device manual in section #16.  
hemostatic agent
- 4. Provide the PMA approval or 510(k) clearance number or attach letters in section #16.
- 5. Does the research involve use of a commercially available device for an unapproved purpose?
- 6. This device research is: Note: Attach documentation/justification in section #16.

Exempt from IDE regulations, (submit required attachments)

Non-Significant risk, (submit required attachments)

Significant risk, (submit required attachments)

The risk determination should be based on the proposed use of a device in an investigation and not on the device alone.

- 7. Provide IDE #. Documentation of IDE # required unless imprinted on sponsor protocol (attach in section #16). See Guidance. exempt
- 8. Who holds the IDE? (Could be manufacturer, study sponsor, or an individual investigator acting as the 'sponsor'). Hemostasis
- 9. If a SLU Investigator is serving as sponsor-investigator of the IDE, click Yes to assure that the additional FDA requirements will be followed. Yes, the additional FDA requirements will be followed.

- 1. Device Name Sinufoam
- 2. Manufacturer Arthrocore
- 3. Describe the device to be used and attach the device manual in section #16.  
hemostatic agent
- 4. Provide the PMA approval or 510(k) clearance number or attach letters in section #16.

**Protocol Title:** Analysis of hemostatic agents compared to physiologic hemostasis

---

- 5. Does the research involve use of a commercially available device for an unapproved purpose?
- 6. This device research is:  
Note: Attach documentation/justification in section #16.
  - Exempt from IDE regulations, (submit required attachments)
  - Non-Significant risk, (submit required attachments)
  - Significant risk, (submit required attachments)

The risk determination should be based on the proposed use of a device in an investigation and not on the device alone.

- 7. Provide IDE #. Documentation of IDE # required unless imprinted on sponsor protocol (attach in section #16). See Guidance. exempt
- 8. Who holds the IDE? (Could be manufacturer, study sponsor, or an individual investigator acting as the 'sponsor'). Arthrocore
- 9. If a SLU Investigator is serving as sponsor-investigator of the IDE, click Yes to assure that the additional FDA requirements will be followed. Yes, the additional FDA requirements will be followed.

- 1. Device Name Nasopore
- 2. Manufacturer Polyganics
- 3. Describe the device to be used and attach the device manual in section #16.  
hemostasis

- 4. Provide the PMA approval or 510(k) clearance number or attach letters in section #16.
- 5. Does the research involve use of a commercially available device for an unapproved purpose?
- 6. This device research is:  
Note: Attach documentation/justification in section #16.
  - Exempt from IDE regulations, (submit required attachments)
  - Non-Significant risk, (submit required attachments)
  - Significant risk, (submit required attachments)

The risk determination should be based on the proposed use of a device in an investigation and not on the device alone.

- 7. Provide IDE #. Documentation of IDE # required unless imprinted on sponsor protocol (attach in section #16). See Guidance. exempt
- 8. Who holds the IDE? (Could be manufacturer, study sponsor, or an individual investigator acting as the 'sponsor'). Polyganics
- 9. If a SLU Investigator is serving as sponsor-investigator of the IDE, click Yes to assure that the additional FDA requirements will be followed. Yes, the additional FDA requirements will be followed.

- 1. Device Name Posisep Hemostat Dressing
- 2. Manufacturer Hemostasis

**Protocol Title:** Analysis of hemostatic agents compared to physiologic hemostasis

---

- 3. Describe the device to be used and attach the device manual in section #16.  
Hemostatic agent
- 4. Provide the PMA approval or 510(k) clearance number or attach letters in section #16.
- 5. Does the research involve use of a commercially available device for an unapproved purpose?
- 6. This device research is: Note: Attach documentation/justification in section #16.
  - Exempt from IDE regulations, (submit required attachments)
  - Non-Significant risk, (submit required attachments)
  - Significant risk, (submit required attachments)

The risk determination should be based on the proposed use of a device in an investigation and not on the device alone.

- 7. Provide IDE #. Documentation of IDE # required unless imprinted on sponsor protocol (attach in section #16). See Guidance. exempt
- 8. Who holds the IDE? (Could be manufacturer, study sponsor, or an individual investigator acting as the 'sponsor'). Hemostasis
- 9. If a SLU Investigator is serving as sponsor-investigator of the IDE, click Yes to assure that the additional FDA requirements will be followed. Yes, the additional FDA requirements will be followed.

- 1. Device Name Posisep X Hemostat Dressing
- 2. Manufacturer Hemostasis
- 3. Describe the device to be used and attach the device manual in section #16.  
Hemostatic agent
- 4. Provide the PMA approval or 510(k) clearance number or attach letters in section #16.
- 5. Does the research involve use of a commercially available device for an unapproved purpose?
- 6. This device research is: Note: Attach documentation/justification in section #16.
  - Exempt from IDE regulations, (submit required attachments)
  - Non-Significant risk, (submit required attachments)
  - Significant risk, (submit required attachments)

The risk determination should be based on the proposed use of a device in an investigation and not on the device alone.

- 7. Provide IDE #. Documentation of IDE # required unless imprinted on sponsor protocol (attach in section #16). See Guidance. exempt
- 8. Who holds the IDE? (Could be manufacturer, study sponsor, or an individual investigator acting as the 'sponsor'). Hemostasis

**Protocol Title:** Analysis of hemostatic agents compared to physiologic hemostasis

---

9. If a SLU Investigator is serving as sponsor-investigator of the IDE, click Yes to assure that the additional FDA requirements will be followed. Yes, the additional FDA requirements will be followed.
- 

